#### 4. Interventions

The intervention scheme of this trial is based on our previous trials regarding acupuncture for functional constipation. Acupuncturists who had an acupuncture license and at least 2 years of clinical experience in acupuncture will perform the treatment. We will use disposable acupuncture needles (of the following sizes: 0.30 × 40, 0.30 × 50 and 0.30 × 75 mm) and SDZ-V EA apparatus (all Hwato Brand, Suzhou Medical Appliance Factory, Suzhou, China) in this trial. The duration of the trial for each participant will be 17 weeks: 1- week baseline assessment (run-out period), 8- week treatment and 8- week follow- up.

### 4.1 EA

Bilateral Tianshu (ST25), Fujie (SP14), Shangjuxu (ST37) will be used in the EA group. The location of the acupoints will be based on Nomenclature and location of acupuncture points drafted in 2006 by the National Standard of the People's Republic of China (GB/T 12346–2006). The local skin will be routinely sterilized while the patient is in a supine position. For ST25 and SP14, 0.30×50 mm or 0.30×75 mm needles will be gently vertically inserted to the muscle layer of the abdominal wall, where patients will feel sharp pain and acupuncturists will feel resistance from the needle tip. For ST37, 0.30×40 mm needles will be vertically inserted approximately 15 mm deep, followed by three-time manipulation of even lifting and twisting method to elicit the sensation of deqi. Paired alligator clips of the EA apparatus will then be attached to the needle holders of the bilateral ST25, SP14, and ST37. The stimulation will be retained for 30 minutes, with

a continuous wave of 10 Hz and current intensity of 0.5 to 4 mA. All needles will be

removed after 30 minutes and pressure will be applied using a dry sterilized cotton ball to

avoid bleeding. Patients will be followed up for another 8 weeks after the treatment

stopped.

4.2 SA

The patients in the SA group will receive minimal needling at non-acupoints as bilateral

sham ST25, SP14, and ST37. The sham ST25 and SP14 are located 2 cm horizontally

outward of the points stimulaed in the EA group. The sham ST37 point is located outward

of ST37 in the middle of the stomach and gallbladder channel. After sterilization of the

skin, 0.30×40 mm needles will be directly inserted about 2 -3 mm until they can stand up

when attached by the alligator clips. No manipulation will be used and no degi sensation

will be elicited at any of the sham points. The bilateral sham ST25, SP14, and ST37

points will be attached by the same EA apparatus with a continuous wave of 10 Hz and

current intensity of 0.1 to 0.2 mA for 30 minutes with only the initial 30 seconds on.

Patients in both groups will receive 24 treatment sessions over an 8-week period (3)

sessions each week, ideally every other day). Each session will last for 30 minutes.

Patients will be treated separately to prevent between-patient communication. Patients

will be followed up for another 8 weeks after the treatment stopped.

4.3 Rescue medication

During the trial, other medication or intervention for OIC will be discouraged. However,

if a patient has no bowel movement for 72 consecutive hours and cannot tolerate it, only

bisacodyl (5 to 10 mg; up to 20 mg per day) or a 110ml glycerol enema will be permitted

as a rescue medication. Details of drug use (time and frequency) will be recorded.

5. Informed consent

### 6. Quality Control

All staff members will undergo training prior to the trial. Monitors will check the case report forms and the acupuncture operation regularly. To improve adherence to intervention protocols, the majority of patients will come from the inpatient setting. The outcomes will be evaluated by independent assessors who are unaware of the group allocation. The data will be input by a clinical research coordinator according to the contents of CRF using the Electronic Data Capture System (EDC), which will be monitored by Clinical Research Associate. Detailed documentation of drop-outs and withdrawals, including the reasons, will be obtained throughout the trial. All of the

investigators will always maintain a strict privacy policy to protect confidentiality before, during and after the trial.

### 7. Data Management

### 7.1 The Raw Data Management and Archiving

We use Electronic Data Capture System (EDC) system to perform data entry. The research assistants will fill out all the electrical CRF through RDC system. Researchers will inspect the eCRF, and signed electrically for the eCRF going into effect. The eCRF and the trace of eCRF revising will be left in the Oracle database.

### 7.2 Data Entry and Storage

### 7.2.1 Database Building and Testing, Data Entry Interface

The eCRF will be noted through CDISC SDTM standard, and the data entry interface will be generated through the Oracle Clinical software. The data entry interface should be in accordance with the paper-version CRF as far as possible. The inputted data will be stored in the Oracle database.

After preliminarily setting up the database, the entry clerks will input some analog data according to the CRF to test the database. The testing contains: (1) the agreement of the data entry interface and the paper-version CRF; (2) the agreement of the exported data from the database and the analog data; (3) the agreement of the structure of the exported database and the paper-version CRF. After the testing, data administrators should revise the database and make a testing report. Then they electrically signed on the approval page of the database to indicate that the testing is completed. The electrical files of the analog CRF, Noted CRF, screenshot of the data entry interface, database testing report, and the approval page of the database should be saved. If the database updates during the trial, the electrical files mentioned above are also need to be updated.

### 7.2.2 Data Entry and Inspection

The research assistants take charge of the data entry for our trial. Before the entry, all the research assistants will accept the related training according to the data entry handbook. Researchers will inspect the database, and then sign electrically to let the data go in to effect.

### 7.3 Data Verification and Problems Solving

Researchers will verify the data through Data Verification Plan (DVP) approved by the data administrator and the statisticians. Data queries will be inputted to a data query database, and form the DCF. After being inspected, the DCF will then be handed back to the original site, and the researchers of the site should answer the queries. Any revision of the database will be recorded through the RDC software.

### 7.4 Medical Coding

A data administrator who has the medicine background will take charge of the medical coding. The contents of the coding are the clinical history, adverse events, and combined medication. The clinical history and adverse events will be coded through MedDRA dictionary (Version 13.0), and the combined medication will be coded via WHO DD dictionary (Version 2007.03). The lead researchers will verify the coded e-files.

### 7.5 Data Report

Data report contains the aspects as followed: (1) members of the project; (2) disagreement from the primary data management plan; (3) actual finish time of every project; (4) problems and the solution during the data management (if have any); (5) reconstruction of the database (if have any); (6) distribution of the participants; (7) participants who disobey the trial protocol; (7) classifying plan of the statistical analysis population.

Data report will be performed monthly since the first entry of the eCRF.

### 7.6 Data Auditing

When the data checking is finished, a data auditing and blinding review meeting will be hold. On the meeting, the data administrators, statisticians, researchers, clinical inspectors, and other related members would have a discussion on the following items according to the data management report and the data lists:

- Distribution of the participants;
- Protocol disobeying or not;
- Possible outlier;
- Baseline data;
- Outcomes;
- Statistical analysis plan.

### 7.7 Database Locking

The database will be locked if it fulfills all the aspects as followed: All the queries have been solved, and the database has been updated; No query has been found through the data inspection; The medical coding has been completed; The plan of the participants 'classification has been approved; The final draft of the SAP has been made, and approved by the project leader.

The statisticians and the data administrators will signed the data locking form, and then the database will be locked. The locked database will be sent to the statisticians for further statistical analysis through the data format of SAS.

### 8. Statistical Consideration

The following is an overview of the statistical considerations. Details of the pre-specified statistical analyses can be found in the Statistical Analysis Plan (SAP).

### 8.1 Statistical Analysis

The primary study hypothesis is that EA is more effective than SA in the treatment of OIC in patients with cancer. The primary outcome is the proportion of responders, defined as a patient that has  $\geq 3$  SBMs/wk and  $\geq$  increase of 1 SBM from baseline simultaneously for at least 6 out of 8 weeks of the treatment period. The primary analysis will be intention-to-treat, which is defined as all randomized participants.

The following secondary outcomes will be analyzed using the t test, repeated measures analysis, Wilcoxon rank-sum test, Chi-square test or Fisher's exact test, as appropriate: A two-side test with p<0.05 will be considered significant for all analyses.

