### 2.4.4.2 Secondary Outcomes

- (1) Changes in the mean weekly SBMs from the baseline during weeks 1-8 and weeks 13-16. The mean weekly SBMs equals the total frequency of SBMs divided by the numbers of week(s) recorded. Assessment time frame: at baseline, over weeks 1-8 and 13-16.
- (2) The proportion of patients with ≥3 mean weekly SBMs during weeks 1-8 and weeks 13-16. Assessment time frame: at baseline, over weeks 1-8 and 13-16.
- (3) The proportion of patients with an increase of ≥1 mean weekly SBM from the baseline during weeks 1-8 and weeks 13-16. Assessment time frame: at baseline, over weeks 1-8 and 13-16.
- (4) A change in the mean weekly CSBMs from the baseline during weeks 1-8 and weeks 13-16. A CSBM is defined as an SBM with the feeling of complete evacuation. The mean weekly CSBMs equals the total frequency of CSBMs divided by number of week(s)

recorded. Assessment time frame: at baseline, over weeks 1-8 and 13-16.

- (5) The proportion of patients with ≥3 mean weekly CSBMs during weeks 1-8 and weeks 13-16. Assessment time frame: at baseline, over weeks 1-8 and 13-16.
- (6) The proportion of patients with an increase of ≥1 mean weekly CSBM from the baseline during weeks 1-8 and weeks 13-16. Assessment time frame: at baseline, over weeks 1-8 and 13-16.
- (7) A change in the mean Bristol Stool Form Scale score for stool consistency of SBMs from the baseline during weeks 1-8 and weeks 13-16. For stool consistency, each patient will be asked to record their stool consistency according to the Bristol Stool Form Scale on the following seven points scale (scored from 1 to 7 for stool types 1 to 7, respectively). Assessment time frame: at baseline, over weeks 1-8 and 13-16.

- Type 1: Separate hard lumps, like nuts (hard to pass)
- Type 2: Sausage-shaped, but lumpy
- Type 3: Like a sausage but with cracks on its surface
- Type 4: Like a sausage or snake, smooth and soft
- Type 5: Soft blobs with clear cut edges (passed easily)
- Type 6: Fluffy pieces with ragged edges, a mushy stool
- Type 7: Watery, no solid pieces. Entirely liquid

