- (8) A change in the mean score for the straining of SBMs from the baseline during weeks 1-8 and weeks 13-16. For assessment of the straining of SBMs, each patient will be asked to rate his/her score of straining, using the following five-point scale: not at all difficult (0), a little bit difficult (1), moderately difficult (2), quite a bit difficult (3), extremely difficult (4). Assessment time frame: baseline, over weeks 1-8 and 13-16.
  - (9)A change in the total and subscale score of the Patient Assessment of

Constipation-Symptom (PAC-SYM) questionnaire from the baseline at weeks 8 and 16. The PAC-SYM is a questionnaire used to evaluate the severity of chronic constipation in the past 2 weeks. It consists of 12 items, which are subdivided into abdominal (4 items), rectal (3 items), and stool (5 items) scales.34 36 The score of each item ranges from 0 to 4, with 0 = symptom absent, 1 = mild, 2 = moderate, 3 = severe and 4 = very severe. Lower scores indicate a lower symptom burden. Each subscale score will be calculated as the mean of the completed items for that subscale. The total score will be calculated as the mean of all completed items. In this trial, the Chinese version of PAC-SYM, which has been validated to have a satisfactory psychometric property, will be used. Assessment time frame: at baseline, at weeks 8 and 16.

- (10) A change in the total and subscale scores of the Patient Assessment of Constipation-Quality of Life (PAC-QOL) questionnaires from the baseline at weeks 8 and 16. The PAC-QOL is a 28-item self-reported questionnaire to assess the burden of constipation on patients' everyday functioning and well-being in the 2 weeks (14 days) prior to assessment. This questionnaire is divided into four subscales: physical discomfort (items 1-4), psychosocial discomfort (items 5-12), worries/concerns (items 13-23), and satisfaction (items 24 to 28). Each of the item scores ranges from 0 (not at all) to 4 (extreme), with lower scores indicating a better quality of life. For each visit, individual subscale scores will be calculated as the mean of the completed items for that subscale. The total score will be calculated as the mean of all of the completed items. We will use the Chinese version of this test in our trial, which has been demonstrated to be a reliable and valid tool. Assessment time frame: at baseline, at weeks 8 and 16.

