- (11) Patients' global assessment of treatment efficacy. Each patient will be asked to rate his/her efficacy of treatment using the following 7-point self-reporting scale: markedly worse (1), moderately worse (2), slightly worse (3), no change (4), slightly improved (5), moderately improved (6), markedly improved (7). Scales with seven response categories are easy to use and have shown a high reliability and validity. This questionnaire will be completed at week 8 and week 16. Assessment time frame: baseline, at weeks 8 and 16.
- (12) The proportion of patients using rescue medicine and the mean frequency of rescue medicine use per week during weeks 1-8 and weeks 9-16. Assessment time frame: at baseline, over weeks 1-8 and 13-16.

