4.4 Statistical Analyses

4.4.1 The General Principle

Summary tables (descriptive statistics and/or frequency tables) will be provided for all variables at different endpoints. For continuous variables, means and standard deviations will be presented, unless the variable has a skewed distribution, in which case medians, 25th and 75th percentiles will be presented. For categorical variables, the number and percentage of participants within each category will be presented. For each variable (continuous or categorical), the number of missing values will be reported.

Statistical Comparisons Between Groups

Continuous variables will be compared using a two-sample *t*-test or Wilcoxon rank-sum test if data show serious deviations from a normal distribution. Categorical data or ordinal data will be compared using a Wilcoxon rank-sum test, chi-square test or Fisher's exact test, as appropriate. All tests will be two-sided.

For the analysis of the primary and secondary outcomes, estimated treatment differences and associated 95% two-sided confidence intervals will be presented.

Analysis Software

For all statistical analyses, SAS 9.4 software will be used. All hypothesis testing will be carried out at the 5% (2-sided) significance level.

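### The 5% significance rule covers all analyses, so up to 40 unadjusted secondary comparisons can be called significant, with no testing order or exploratory label

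*Protocol*

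**What the plan says.** Protocol 8.1 names the primary outcome, introduces the tests for the secondary outcomes, and then states the rule: "A two-side test with p<0.05 will be considered significant for all analyses". SAP 4.4.1 says the same: "All hypothesis testing will be carried out at the 5% (2-sided) significance level". It also plans effect estimates for both tiers: "For the analysis of the primary and secondary outcomes, estimated treatment differences and associated 95% two-sided confidence intervals will be presented".

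Protocol 2.4.4.2 lists twelve secondary items. Most are assessed over two windows or at two visits, for example "Changes in the mean weekly SBMs from the baseline during weeks 1-8 and weeks 13-16". Several contain more than one measure. On PAC-SYM the protocol writes "It consists of 12 items, which are subdivided into abdominal (4 items), rectal (3 items), and stool (5 items) scales", and the total score is analysed as well. PAC-QOL has a total and four subscales. The rescue item is "The proportion of patients using rescue medicine and the mean frequency of rescue medicine use per week during weeks 1-8 and weeks 9-16".

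SAP 4.4.4, the section on secondary outcomes, adds only the analysis population, the absence of imputation, and descriptive formats. Neither document contains a multiplicity adjustment, a testing order, a condition on the primary result, or a statement that secondary results are exploratory. The one group of results made descriptive only is adverse events (SAP section 5, Table 1, change 3).

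**The concern.** Leaving secondary p-values unadjusted is common and defensible when the plan says they are supportive. This plan does not say so. Its rule is positive and general: any test below 0.05 is significant, whether it is the responder comparison or one PAC-QOL subscale at week 16.

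What is at stake is the wording of the report. If the primary result is null or marginal, the plan as written still allows significant benefits to be stated for individual bowel-movement, symptom or quality-of-life measures. Those measures would come from a long list, and the reader would have no prespecified basis for discounting them. The primary outcome covers only the eight treatment weeks, so any statement about the period after treatment could come only from this unprotected list.

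**Working it through.** **The plan's own figure.** The documents state no error rate across secondary outcomes. The only related figure is the sample size in Protocol 2.4.1.3: 14% sham response, a difference of 31.4 points (so 45.4% with EA), 90% power, two-sided 0.05, and 20% loss. The unpooled formula per arm is

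(1.960 + 1.282)² × (0.14 × 0.86 + 0.454 × 0.546) / 0.314² = 39.2, so 40.

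Then 40 / 0.80 = 50 per arm, or 100 in total, as stated. This figure belongs to the primary outcome alone and is not affected by this point.

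**Count of secondary comparisons (Protocol 2.4.4.2).**

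| Items | Measures | Windows or visits | Comparisons |
|---|---|---|---|
| (1)–(8) SBM ×3, CSBM ×3, stool form, straining | 8 | 2 | 16 |
| (9) PAC-SYM total + 3 subscales | 4 | 2 | 8 |
| (10) PAC-QOL total + 4 subscales | 5 | 2 | 10 |
| (11) Global assessment | 1 | 2 | 2 |
| (12) Rescue medicine: proportion, frequency | 2 | 2 | 4 |
| **Total** | **20** | | **40** |

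Item (12) gives its follow-up window first as weeks 9-16 and then as weeks 13-16; the count is the same either way. Protocol 8.1 also lists repeated measures analysis. If that gave one test per measure, there would be 20 tests. The count leaves out the other prespecified outcomes (13)–(16), the baseline comparisons in SAP 4.4.2 and the opioid-dose interaction in SAP 4.4.3, all of which a rule for all analyses could also cover.

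**Expected false positives when EA has no effect on any of these outcomes.** 40 × 0.05 = 2, or 20 × 0.05 = 1. This holds whatever the correlation.

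**Chance of at least one.** Under independence it is 1 − 0.95⁴⁰ = 0.871, and 1 − 0.95²⁰ = 0.642. With a common correlation ρ, each test statistic is modelled as √ρ·U + √(1−ρ)·E, with U shared and E separate standard normal variables. The chance that any |z| exceeds 1.96 is then found by integrating over U. The values of ρ are assumptions.

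| ρ | 40 tests | 20 tests |
|---|---|---|
| 0 (independence) | 87.1% | 64.2% |
| 0.3 | 74.5% | 54.0% |
| 0.5 | 57.1% | 41.9% |
| 0.6 | 47.3% | 35.4% |
| 0.7 | 37.5% | 28.9% |
| 0.9 | 18.4% | 15.5% |

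A simulation of 200,000 draws for 40 tests agrees to within about 0.2 points (74.7%, 57.2%, 47.4%, 37.4% and 18.5% for ρ from 0.3 to 0.9). Grouping the 40 tests into domains, with higher correlation within a domain than between domains, gives about 75% at 0.5/0.2, 58% at 0.7/0.4 and 48% at 0.8/0.5.

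**Why independence is out of reach here.** Items (2) and (3) are cut-offs of the same mean weekly SBM count as item (1), and items (5) and (6) repeat this for CSBMs. A CSBM is by definition an SBM. Questionnaire totals average the same items as their subscales. Each measure is taken twice in the same patients.

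**The case against.** The strongest reply is that the hierarchy is already clear. There is one primary outcome, one statistical null hypothesis on responders (SAP 4.2), and a sample size built on that outcome alone. Everything else is headed secondary or other. On this reading the 5% sentence only sets sidedness and a nominal threshold, and nobody says a secondary result can stand in for a null primary. Much of this stands. A reader might infer that the trial's main error rate is inflated; it is not. But a ranking by heading does not limit what may be called significant, and the rule in both documents expressly reaches the secondary outcomes.

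A reader might also infer that a false significant finding is likely, and quote 87%. The documents do not support that. The figure needs independence, which the outcome definitions exclude. At a common correlation of 0.6 the chance for 40 tests is already below one half, and 20 tests at 0.5 give 42%.

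A third inference would be that the plan makes a claim of lasting benefit. It does not. The objective and hypotheses are silent on durability, and the long-term effect in Protocol 2.2 is background from functional constipation.

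Finally, an unadjusted 95% interval that excludes zero tells the reader much the same as p<0.05. That is correct. Dropping the word significant does not lower the false-positive rate; it limits what the trial may conclude. So the intervals must themselves be described as unadjusted.

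**Conclusion.** The point holds as a fault in what the plan allows to be claimed. Following both documents as written would permit significance statements from up to 40 secondary comparisons (about 20 under a one-test-per-measure repeated measures analysis), with no protection and no exploratory label. With no true effect, about 2 of 40 would be significant by chance.

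The chance of at least one runs from about 75% down to 18% for 40 tests, and from 54% down to 15.5% for 20 tests, as the common correlation goes from 0.3 to 0.9. All of these are well above 5%. They rest on assumed correlations, on equal correlation between all pairs, and on no effect for any secondary outcome. Whether the chance exceeds one half is not established. The primary test and the sample size are unaffected. The change is worth making, but it does not threaten the trial's main conclusion.

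**What to change.** In Protocol 8.1 and SAP 4.4.1, limit the 5% significance claim to the primary outcome. For secondary and other outcomes, report estimates with 95% confidence intervals, which SAP 4.4.1 already plans for the secondary outcomes. State that the intervals and any p-values are not adjusted for multiplicity, and that the results will be interpreted as exploratory.

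The cost is about one sentence in each document, with no new data, patients or models. The downside is that no secondary result can then be called statistically significant. If the sponsor wants to keep that option for a few key secondary outcomes, naming them and prespecifying a testing order or a Holm procedure is an acceptable alternative, with the rest treated as above.
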